3. OBJECTIVES AND ENDPOINTS

	Objectives	Endpoints			
Pri	Primary				
•	To assess the safety and reactogenicity of Ad26.RSV.preF-based RSV vaccine in healthy adults aged 18 to 59 years	 Solicited local (injection site) and systemic AEs for 7 days after vaccination Unsolicited AEs for 28 days after vaccination Serious adverse events (SAEs) and adverse events of special interest (AESIs) until 6 months after vaccination 			
•	To assess the safety and reactogenicity of Ad26.RSV.preF-based RSV vaccine in adults aged 18 to 59 years at high-risk of severe RSV disease	 Solicited local (injection site) and systemic AEs for 7 days after vaccination Unsolicited AEs for 28 days after vaccination SAEs and AESIs until 6 months after vaccination 			

Objectives	Endpoints
• If non-inferiority is demonstrated in adults: To demonstrate the non-inferiority of the humoral response to the administration of Ad26.RSV.preF-based vaccine in high-risk adults aged 18 to 59 years versus in adults aged 65 years and older	 Neutralizing antibody titers against RSV A2 strain at 14 days after vaccination Seroresponse rate* at 14 days after vaccination as determined by neutralization assay (VNA-A2).

^{*} Seroresponse is defined as a 4 fold increase from baseline in Day 15 antibody titers.

Sec	Secondary				
•	Investigate the vaccine-induced immune responses post-vaccination	Pre-F ELISA antibody titers at 14 days after vaccination			
Exp	Exploratory				
•	To assess the persistence of immune response post-vaccination	 Pre-F ELISA antibody titers at 6 months after vaccination Neutralizing antibody titers against RSV A2 strain at 6 months after vaccination 			
•	To further explore the humoral immune responses elicited by the Ad26.RSV.preF-based vaccine	 Neutralizing antibody titers against RSV B strains and other RSV A strains Neutralizing antibody titers against Ad26 Molecular and functional antibody characterization including antibody avidity, Fc-mediated effector function, subtyping and isotyping, glycosylation patterns, antibody sequencing for repertoire[†] 			
•	To explore the cellular immune responses elicited by the Ad26.RSV.preF-based vaccine in a subset of participants (ie, the Cellular Immuno Subset)	• RSV-F specific interferon gamma (IFN-γ) enzyme-linked immunospot (ELISpot) and detailed immunoprofiling which may include analysis of T-cell and B-cell responses to RSV F protein peptidestimulated peripheral blood mononuclear cell (PBMC) (including, but not limited to, CD4+/CD8+, Th1/Th2, IL-2, IFN-γ, TNF-α, activation markers and memory markers) using flow cytometry or mass cytometry			

[†] Exploratory endpoints are optional. Exploratory assessments are based on the outcome of ongoing testing in other studies. Some testing may not be performed or reported.

Refer to Section 8 for evaluations related to endpoints.

HYPOTHESES

To demonstrate the non-inferiority of the humoral immune response to Ad26/protein preF RSV vaccine in all adults aged 18 to 59 years (Group 1+3) versus in adults aged 65 years and older (Group 5) and in high-risk adults aged 18 to 59 years (Group 3) versus in adults aged 65 years and older (Group 5) in terms of neutralizing antibody GMTs and seroresponse rates.

The following hypotheses will be tested sequentially:

Null Hypothesis 1:

• Ad26/protein preF RSV vaccine induces inferior humoral response in terms of VNA A2 antibody GMTs at Day 15 in adults aged 18 to 59 years (Groups 1 and 3) versus in adults aged 65 years and older (Group 5).

OR

• Ad26/protein preF RSV vaccine induces inferior humoral immune response in terms of seroresponse rates of VNA A2 antibody titers at Day 15 in adults aged 18 to 59 years (Groups 1 and 3) versus in adults aged 65 years and older (Group 5).

Alternative Hypothesis 1:

• Ad26/protein preF RSV vaccine induces non-inferior humoral responses in terms of VNA A2 antibody GMTs at Day 15 in adults aged 18 to 59 years (Groups 1 and 3) versus in adults aged 65 years and older (Group 5).

AND

• Ad26/protein preF RSV vaccine induces non-inferior humoral responses in terms of seroresponse rates of VNA A2 antibody titers at Day 15 in adults aged 18 to 59 years (Groups 1 and 3) versus in adults aged 65 years and older (Group 5).

Success Criterion 1 (All Adults):

Non-inferiority of immune response in all adults is demonstrated:

• if the lower limit of the 2-sided 95% confidence interval (CI) for the VNA A2 GMT ratio of all adults aged 18 to 59 years versus in adults aged 65 years and older (GMT_{Group 1+3}/GMT_{Group 5}) is >0.67.

AND

• if the lower limit of the 2-sided 95% CI for the seroresponse rate difference of all adults aged 18 to 59 years versus in adults aged 65 years and older (Seroresponse Rate _{Group 1+3} Seroresponse Rate _{Group 5}) based on the VNA A2 antibody titers is >-0.1

If non-inferiority is demonstrated in all adults for both neutralizing antibody GMTs and seroresponse rates, then the following hypothesis will be tested:

Null Hypothesis 2:

• Ad26/protein preF RSV vaccine induces inferior humoral response in terms of VNA A2 antibody GMTs at Day 15 in high-risk adults aged 18 to 59 years (Group 3) versus in adults aged 65 years and older (Group 5).

OR

• Ad26/protein preF RSV vaccine induces inferior humoral response in terms of seroresponse rates of VNA A2 antibody titers at Day 15 in high-risk adults aged 18 to 59 years (Group 3) versus in adults aged 65 years and older (Group 5).

Alternative Hypothesis 2:

• Ad26/protein preF RSV vaccine induces non- inferior humoral response in terms of VNA A2 antibody GMTs at Day 15 in high-risk adults aged 18 to 59 years (Group 3) versus in adults aged 65 years and older (Group 5).

AND

• Ad26/protein preF RSV vaccine induces non-inferior humoral response in terms of seroresponse rates of VNA A2 antibody titers at Day 15 in high-risk adults aged 18 to 59 years (Groups 3) versus in adults aged 65 years and older (Group 5).

Success Criterion 2 (High-risk Adults):

Non-inferiority of immune response in high-risk adults is demonstrated:

• if the lower limit of the 2-sided 95% CI for the VNA A2 GMT ratio of high-risk adults aged 18 to 59 years versus in adults aged 65 years and older (GMT_{Group 3}/GMT_{Group 5}) is >0.67.

AND

• if the lower limit of the 2-sided 95% CI for the seroresponse rate difference of high-risk adults aged 18 to 59 years versus in adults aged 65 years and older (Seroresponse Rate _{Group 3} Seroresponse Rate _{Group 5}) based on the VNA A2 antibody titers is >-0.1.

4. STUDY DESIGN

4.1. Overall Design

This is a randomized, double-blind, placebo-controlled, multicenter, interventional Phase 3 study to evaluate the safety and immunogenicity of the Ad26/protein preF RSV vaccine in adults aged 18 to 59 years, including those who are at high-risk of severe RSV disease. A cohort of adults aged 65 years and older will also be included. A target of 1,113 participants will be enrolled: 385 healthy adults aged 18 to 59 years will be enrolled in Cohort 1 and randomized in a 9:2 ratio to receive Ad26/protein preF RSV vaccine or placebo; 385 high-risk adults aged 18 to 59 years will be enrolled in Cohort 2 and randomized in a 9:2 ratio to receive Ad26/protein preF RSV vaccine or placebo, 343 adults aged 65 years and older will be enrolled in Cohort 3 and randomized in a 45:4 ratio to receive Ad26/protein preF RSV vaccine or placebo (see Table 1). The study vaccine will be administered as a single IM injection.

Participants will be stratified for COVID-19 vaccine administration (3 categories: 1. Janssen COVID-19 vaccine, 2. Vaxzevria[®] [Oxford/AstraZeneca], 3. other vaccine, or no vaccine).

Table 1: Overview of the Cohorts, Groups, and Targeted Number of Participants				
Cohort		Group	N	Day 1 (Vaccination)
1	healthy adults, 18 to 59 years	1	315	Ad26.RSV.preF 1×10 ¹¹ vp + RSV preF protein 150 μg
		2	70	Placebo
2	high-risk adults, 18 to 59 years ^a	3	315	Ad26.RSV.preF 1×10 ¹¹ vp + RSV preF protein 150 μg
		4	70	Placebo
3	adults, 65 years and older	5	315	Ad26.RSV.preF 1×10 ¹¹ vp + RSV preF protein 150 μg
		6	28	Placebo

N = number of participants, vp = virus particles.

In all cohorts, participants will be stratified for COVID-19 vaccine administration.

All cohorts will be enrolled in parallel. Enrollment in Spain will be limited to Cohorts 2 and 3.

Safety and humoral immunogenicity assessments will be performed for all participants (see Section 9.2.1 for the sample size determination).

For a subset of the participants, additional cellular immunogenicity assessments will be performed. This subset will be referred to as the Cellular Immuno Subset and will consist of approximately 63 active study vaccine participants and approximately 7 placebo participants per cohort. The Cellular Immuno Subset will be recruited in specific study sites.

After vaccination, participants will remain under observation at the study site for at least 30 minutes for presence of any acute reactions and solicited events. Any unsolicited AEs, solicited local (injection site) or systemic AEs, and vital signs (systolic and diastolic blood pressure [sitting], heart rate, respiratory rate, and body temperature) will be documented by study-site personnel following this observation period. In addition, participants will record solicited signs and symptoms in a participant diary beginning on the evening of the day of vaccination and on a daily basis for 7 days post-vaccination (Section 8).

The reporting periods of AEs, SAEs, and AESIs are detailed in Section 8.3. Reporting periods for concomitant therapy are outlined in Section 6.8.

Blood will be collected from all participants to assess humoral immune responses pre-vaccination and at 14 days and 6 months post-vaccination. Additional blood will be collected from the Cellular Immuno Subset to assess cellular immune responses pre-vaccination and at 14 days and 6 months post-vaccination.

Safety issues that might arise from this study may be escalated to an Independent Data Monitoring Committee, as needed.

The study duration will be approximately 6 months per participant. The study comprises screening (pre-vaccination) and vaccination for each participant on Day 1, and a 6-month safety and immunogenicity follow-up period. The end of the study is defined as the last participant's last visit.

Over the entire study, approximately 60 mL blood will be collected from each participant to assess humoral immune responses. In addition, approximately 120 mL will be collected from each

participant in the Cellular Immuno Subset to assess cellular immune responses. The total blood volume to be collected from participants in the Cellular Immuno Subset will be approximately 180 mL.

Unscheduled study visits may be performed based on investigator's clinical judgment and may include further evaluations, as needed.

A diagram of the study design is provided in Section 1.2 (Figure 1). Further details are provided in the Schedule of Activities.

4.2. Scientific Rationale for Study Design

For the rationale for performing this study, refer to Section 2.1.

Blinding and Control

A placebo control will be used to establish the frequency and magnitude of changes in clinical endpoints that may occur in the absence of active study vaccine in Cohorts 1 and 2. Safety of the vaccine in older adults has been established in the VAC18193RSV2001 study, therefore only a small placebo control group is added for blinding purposes. Within a cohort, randomization will be used to minimize bias in the assignment of participants to vaccination groups (active or placebo), to increase the likelihood that known and unknown participant attributes (eg, demographic and baseline characteristics) are evenly balanced across vaccination groups. Blinded vaccine will be used to reduce potential bias during data collection and evaluation of safety endpoints.

Vaccination Groups

The dose of each vaccine will be identical in the active groups (Groups 1, 3 and 5). Groups 2, 4 and 6 will receive placebo.

Vaccine Component Selection

The rationale behind the selection of the Ad26/protein preF RSV vaccine is described in Section 2.2 and in the IB for Ad26/protein preF RSV vaccine (IB Ad26/protein preF RSV vaccine 2021).

Dose Level Selection

The rationale behind the dose level selection for the Ad26/protein preF RSV vaccine is described in Section 4.3.

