6.3. Measures to Minimize Bias: Randomization and Blinding

Study Vaccine Allocation

Procedures for Randomization

Central randomization will be implemented in this study. Participants will be randomly assigned to a vaccination group based on a computer-generated randomization schedule prepared before the study by or under the supervision of the sponsor. The randomization will be balanced by using randomly permuted blocks.

The randomization will be stratified based on the COVID-19 administration vaccine (3 categories: 1. Janssen Covid-19 vaccine, 2. Vaxzevria (Oxford/AstraZeneca), 3. other vaccine or no vaccine).

Sites will be split into 2 categories based on their PBMC collection capabilities for enrolment in the Cellular Immuno Subset.

For Cohorts 1 and 2, sites collecting PBMC samples will initially randomize participants in the Cellular Immuno Subset of the respective cohort according to a 9:1 ratio (active: placebo). When the Cellular Immuno Subset has been completed for a cohort (70 participants per cohort), the sites will keep randomizing the remaining participants of that cohort according to a 4:1 ratio (active: placebo). Sites with no PBMC sample collection capabilities will randomize participants that are not part of the Cellular Immuno Subset (from whom only humoral samples will be collected) of the respective cohort according to a 4:1 ratio (active: placebo).

For Cohort 3, sites collecting PBMC samples will initially randomize participants in the Cellular Immuno Subset according to a 9:1 ratio (active: placebo). When the Cellular Immuno Subset has been completed (70 participants), the sites will keep randomizing the remaining participants of that cohort according to a 12:1 ratio (active: placebo). Sites with no PBMC sample collection capabilities will only randomize participants that are not part of the Cellular Immuno Subset (from whom only humoral samples will be collected) according to a 12:1 ratio (active: placebo).

In this way, the overall randomization ratio in Cohorts 1 and 2 is 9:2 (active:placebo) and 45:4 (active:placebo) in Cohort 3.

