9.2. Sample Size Determination

9.2.1. Immunogenicity

Immunogenicity assessments will be performed in all participants (N 1,113).

Sample size calculations for the immunogenicity objectives are performed under the following assumptions.

For the humoral immune response in terms of neutralizing antibody GMTs:

• no difference between high-risk adults aged 18 to 59 years and adults aged 65 years and older and no difference between high-risk adults aged 18 to 59 years and adults aged 65 years and older (ie, assuming a true GMT ratio of Day 15 [ie, 14 days after vaccination] RSV A2 neutralizing antibody titers equal to 1 for those comparisons, and similar standard deviation)

- a standard deviation of 1.5 at the log₂ scale for VNA A2 on Day 15^a
- non-inferiority limit of 0.67 (2/3)
- 1-sided α of 2.5%

For the humoral immune response in terms of neutralizing antibody seroresponse rates (defined as a 4-fold increase from baseline in Day 15 antibody titers):

- Seroresponse rates are assumed to be 85% in all adults aged 18 to 59 years, high risk adults aged 18 to 59 years and adults aged 65 years and older, based on available data from Phase 1/2 clinical studies,
- Non-inferiority margin of 10%
- 1-sided α of 2.5%

In addition:

- a ratio of 1:1:1 for the active groups in Cohorts 1, 2, and 3
- hierarchical testing (ie, test first Group 1+3 versus Group 5, if non-inferiority is demonstrated: test Group 3 versus Group 5)

Simulations show that a total of 285 evaluable participants per active group in each cohort are needed to have 90% power to demonstrate non-inferiority in terms of neutralizing antibody GMT and seroresponse rates between high-risk adults aged 18 to 59 years and adults aged 65 years and older. With this sample size, the power to demonstrate non-inferiority in terms of neutralizing antibody GMT and seroresponse rates between all adults aged 18 to 59 years and adults aged 65 years and older is >95%. The power to demonstrate non-inferiority for the high-risk adults aged 18 to 59 years and adults aged 65 years and older is approximately 90%, taking into account the testing strategy (sequential testing). To account for exclusions from the Per-protocol Immunogenicity Set (see Section 9.3), drop-outs, and missing samples, approximately 315 participants per active group should be enrolled.

9.2.2. **Safety**

Solicited AEs, unsolicited AEs SAEs, and AESIs will be collected in all participants (N 1,113).

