Figure 2 shows that with 315 active participants per group (Groups 1 and 3), the observation of 0 events in the database would be associated with 95% confidence that the true rate is less than 1%. When pooling Groups 1 and 3, the observations of 0 events would be associated with 95% confidence that the true rate is less than 0.5%.

Table 6 indicates that with 315 active participants per group (Groups 1 and 3), the probability to observe at least one AE is 96% if the true AE rate at least 1%. When pooling both groups, the probability to observe at least 1 AE is 96% if the true AE rate is at least 0.5%. For Group 5 (active

_

^a Based on Day 15 VNA A2 results obtained from Cohort 2, Group 14 in study VAC18193RSV1004.

participants of the older adults group), safety data is already collected in other studies. Therefore, no additional participants are added on top of what is needed to assess immunogenicity.

[figure not shown]

Figure 2: Upper-Limit of the One-sided 95% CI around the Proportion if no Events are Observed by Number of Participants

Table 6: Probability to Observe at Least One AE by Given True AE Rates

True AE Rate	N=315	N=630
0.5%	79%	96%
1%	96%	100%
2.5%	100%	100%

In Cohorts 1 and 2, a placebo group (Groups 2 and 4) of approximately 70 high-risk adults aged 18 to 59 years and of approximately 70 healthy adults aged 18 to 59 years is added for blinding purposes. In Cohort 3, a placebo group (Group 6) of approximately 28 adults aged 65 years and older is added for blinding purposes. This results in a total sample size of approximately 1,113 participants.

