# 5.4. Primary Safety Endpoint Analysis

Safety endpoints include:

- Solicited local (injection site) and systemic AEs for 7 days after vaccination
- Unsolicited AEs for 28 days after vaccination
- Serious adverse events (SAEs) and adverse events of special interest (AESIs) until 6 months after vaccination

No formal statistical testing of safety data is planned. Safety data will be analyzed descriptively by cohort and group. All safety analyses will be based on the FA Set. Continuous variables will be summarized using the following statistics, as appropriate: number of observations, median, minimum and maximum. Frequencies and percentages (one decimal place) will be generated for categorical variables.

Safety data will be analyzed by study intervention regimens as designed per protocol, per phase and across the entire study period where applicable. For unsolicited AE, denominator for the percentages is the number of participants in the considered population and phase for a certain regimen (incidence per 100 participants/phase). For solicited AEs, the denominator for the percentages is the number of participants with data assessed by the PI in the considered population and phase for a certain and phase for a certain regimen (incidence per 100 participants/phase).

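### The placebo groups in Cohorts 1 and 2 have a stated control role, but no active-minus-placebo difference or interval is planned for any safety endpoint, and the sample size text names only blinding as their purpose

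*Protocol*

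**What the plan says.** **Purpose.** Protocol 4.2, under its paragraph on blinding and control, states for Cohorts 1 and 2: "A placebo control will be used to establish the frequency and magnitude of changes in clinical endpoints" in the absence of active vaccine. It then sets Cohort 3 apart: safety in older adults is already established, "therefore only a small placebo control group is added for blinding purposes". Protocol 9.2.2 uses the same reason for Cohorts 1 and 2. Its sentence opens "In Cohorts 1 and 2, a placebo group (Groups 2 and 4) of approximately 70 high-risk adults aged 18 to 59 years" and continues with a second group "of approximately 70 healthy adults aged 18 to 59 years is added for blinding purposes". The synopsis repeats this.

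**Size.** Protocol 9.2.1 sets "approximately 315 participants per active group should be enrolled". Protocol 6.3 allocates 9:2 overall in Cohorts 1 and 2. It builds that ratio from 9:1 in the Cellular Immuno Subset (70 people per cohort) and 4:1 for everyone else.

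**Analysis.** Safety and reactogenicity in Cohort 1 and in Cohort 2 are primary objectives (Protocol 3). SAP 5.4 says: "No formal statistical testing of safety data is planned. Safety data will be analyzed descriptively by cohort and group". It specifies frequencies and percentages. Neither document plans a risk difference, a risk ratio or a confidence interval for any safety endpoint. Protocol 9.2.2 does give precision in Figure 2 and Table 6, for the active groups alone and for Groups 1 and 3 pooled.

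**The concern.** If placebo is there to show what happens without vaccine, the matching quantity is active minus placebo, with an interval. Randomisation to active or placebo takes place within each cohort, whereas the immunogenicity comparisons are between cohorts and are not randomised. The planned tables put a percentage from about 315 people beside one from about 70 and leave the reader to judge how far chance explains the gap.

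This can mislead in both directions. A few active events against none on placebo may look like an excess when it is ordinary chance. Two similar percentages may look like reassurance when the data are compatible with a difference of several points. The issue is sharpest in Cohort 2. Protocol Appendix 10 accepts coronary disease, myocardial infarction and heart failure as qualifying conditions, and Appendix 9 lists acute myocardial infarction and stroke among the potential AESIs. Some background events are therefore plausible.

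**Working it through.** **Inputs.** Active 315 and placebo 70 per cohort, so 630 and 140 pooled (Protocol 4.1, 9.2). Cellular Immuno Subset about 63 active and 7 placebo per cohort (Protocol 4.1). The documents give no adverse event rates, so every rate below is an assumption.

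**1. The plan's own figures.** The one-sided 95% upper limit with zero events is 1 − 0.05^(1/N). This gives 0.947% at N=315 and 0.474% at N=630, matching the stated limits below 1% and 0.5%. Table 6 uses 1 − (1 − p)^N. At p = 0.5%, 1% and 2.5% this gives 79.4%, 95.8% and 99.97% for N=315, and 95.8%, 99.8% and 100% for N=630. Every cell agrees after rounding.

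**2. The same formulas for placebo.**

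| N | Upper limit, 0 events | P(at least one event) at a 1% rate |
|---|---|---|
| 70 | 4.2% | 50.5% |
| 140 | 2.1% | 75.5% |
| 315 (active) | 0.95% | 95.8% |

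**3. Chance imbalance with equal true rates.** P(at least 3 of 315 active) × (1 − p)^70:
- p = 0.5%: 15%
- p = 1%: 0.611 × 0.495 = 30% (expected events 3.2 active, 0.7 placebo)
- p = 2%: 0.952 × 0.243 = 23% (expected 6.3 and 1.4)
- p = 3%: 12%

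An interval would show this directly. For 3/315 v 0/70 the difference is 1.0 point, with a Newcombe 95% interval of −4.3 to 2.8 points.

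**4. Width of the missing interval.** The 95% half-width is 1.96 × √[p(1 − p)(1/n₁ + 1/n₀)]. At p = 20%, 315 v 70 gives 1.96 × √[0.16 × (1/315 + 1/70)] = 10.4 points, and 630 v 140 gives 7.3 points.

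| Assumed rate in both groups | 5% | 10% | 20% | 30% | 50% |
|---|---|---|---|---|---|
| 315 v 70 | ±5.6 | ±7.8 | ±10.4 | ±11.9 | ±12.9 |
| 630 v 140 | ±4.0 | ±5.5 | ±7.3 | ±8.4 | ±9.2 |

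Large reactogenicity differences would be estimated usefully. With assumed rates of 50% v 20%, the Newcombe interval is 18.0 to 39.6 points per cohort and 21.7 to 37.0 pooled.

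**5. Why allocation stratum matters.** Outside the subset there are 315 − 63 = 252 active and 70 − 7 = 63 placebo recipients, which is 4:1. The subset therefore makes up 63/315 = 20% of active but 7/70 = 10% of placebo recipients. If event rates differ by d points between the subset and the rest, a crude difference is biased by (0.20 − 0.10) × d. For example, d = 10 points gives 1 point of bias.

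Stratifying costs almost nothing. With Mantel-Haenszel weights n₁n₀/(n₁ + n₀), the strata contribute 63 × 7/70 = 6.3 and 252 × 63/315 = 50.4, in total 56.7. The unstratified value is 315 × 70/385 = 57.3. At 20% the half-width is 1.96 × √(0.16/56.7) = 10.4 points per cohort. Pooled over both cohorts it is 1.96 × √(0.16/113.4) = 7.4 points.

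**The case against.** The strongest case for leaving the plan alone has four parts.

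- **The objective is to assess safety, not to compare groups.** Descriptive analysis is stated consistently in both documents. This stands. Nothing here asks for a hypothesis test, and a descriptive difference with an interval is compatible with the SAP wording.
- **A reader can compute the difference from the tables, and table specifications sit in a separate document that is not public.** This stands in part. The published percentages by cohort and group allow only a crude difference, which mixes the two allocation ratios. The choice of estimate and interval belongs in the SAP, which says it holds what is needed for the complete safety analysis.
- **AESIs are not left to raw percentages.** This stands. A chartered committee reviews potential AESIs against the TTS definition (Protocol 10.3.6), and SAP 5.4.1.1 classifies qualified cases by Brighton, CDC or PRAC criteria. Clinically unstable cardiac disease is also excluded. This weakens the AESI argument but does not touch common adverse events.
- **The interval would not settle a modest excess.** This also stands. From a 20% background, the active rate detectable with 80% power (two-sided 5%) is 36.9% per cohort and 31.6% pooled. The interval shows the uncertainty without removing it.

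A reader might also infer that the documents contradict themselves, or that Cohort 1 and 2 placebo exists solely for blinding. The text does not support either reading. The limiting word in Protocol 4.2 concerns Cohort 3, one placebo arm can serve both roles, and 70 per cohort against 28 in Cohort 3 fits a wider role. Nor is it right that safety has no stated precision: the active-group figures are given and are correct.

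**Conclusion.** The point holds as an analysis gap worth closing, joined to a wording inconsistency that is clerical on its own. The randomised active-versus-placebo contrast in Cohorts 1 and 2 is never estimated with its uncertainty, although safety in those cohorts is a primary objective and Protocol 4.2 gives placebo a control role. The gap does not follow from the two purpose statements; it is a separate omission.

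The size rests on assumed rates. The chance of at least three active events with none on placebo is 12% to 30% for equal true rates of 0.5% to 3%, and the three-against-none pattern is an illustrative choice. The placebo limits of 4.2% and 2.1% depend only on group size. No stated figure, sample size or immunogenicity conclusion changes.

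**What to change.** 1. **SAP 5.4:** add an active-minus-placebo risk difference with a 95% confidence interval of score or exact type, labelled descriptive and with no test. Apply it to any and grade 3 or higher solicited local AEs and systemic AEs, any and grade 3 or higher unsolicited AEs to 28 days, and SAEs and potential AESIs to 6 months. Name which of the potential-AESI categories in SAP 5.4.1.1 is used.
2. **Groupings:** report it for Cohort 1, for Cohort 2, and for Groups 1+3 v 2+4. Stratify by allocation stratum (Cellular Immuno Subset 9:1 v others 4:1) within each cohort, and also by cohort in the pooled estimate.
3. **Protocol 9.2.2, beside Table 6:** state that zero events in 70 (140) placebo recipients exclude only rates above 4.2% (2.1%), on the same one-sided 95% convention as Figure 2.
4. **Protocol 4.2, 9.2.2 and synopsis:** use one statement of purpose for the Cohort 1 and 2 placebo groups.

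The cost is SAP and protocol wording and one table, with no extra participants or procedures. The downside is that the intervals will be wide. They will show uncertainty about uncommon events rather than resolve it.
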